APPENDIX 8: List of Abbreviations

ADHD	Attention Deficit Hyperactivity Disorder
ALT	Alanine amino transferase
ANCOVA	Analysis of covariance
Apo	Apolipoprotein
AST	Aspartate amino transferase
BASC-II	Behavior Assessment System for Children, 2 nd ed ⁿ
BRIEF	Behavior Rating Inventory of Executive Function
BUN	Blood urea nitrogen
CADS	Conners ^r ADHD/DSM-IV Scales
CANTAB	Cambridge Neuropsychological Testing Automated Battery
CBC	Complete blood count
COWAT	Controlled Oral Word Association Test
CPK	Creatine phosphokinase
CPT	Continuous Performance Task
CTCAE	Common Terminology Criteria for Adverse Events
DoD	Department of Defense
DSMB	Data and Safety Monitoring Board
DSM-IV	Diagnostic and Statistical Manual of Mental Disorders, 4th ed ⁿ
EAB	External Advisory Board
FDA	Food and Drug Administration
GABA	Gamma-aminobutyric acid
GDP	Guanosine diphosphate
GTP	Guanosine-5'-triphosphate
HDL	High-density lipoproteins
heFH	Hypercholesterolemia
HIPPA	Health Insurance Portability and Accountability Act
HMG CoA	3-hydroxy-3-methyl-glutaryl-Coenzyme A
IQ	Intelligence quotient
IRB	Institutional Review Board
JLO	Judgment of Line Orientation
LDL	Low-density lipoprotein
LTP	Long-term potentiation
MOT	Motor Screening
NF1	Neurofibromatosis type 1
NIH	National Institutes of Health
PAL	Paired Associate Learning
PedsQL	The Pediatric Quality of Life Scale
PPI	Pre-pulse inhibition
RBC	Regression based change
SD	Standard deviation
SGT	Solanidine UDP-glucose glucosyltransferase
SOC	Stockings of Cambridge
SST	Stop Signal Task
SWM	Spatial Working Memory
TEA-Ch	Test of Everyday Attention for Children
UDP-glucose	Uridine diphosphate glucose
VLDL	Very low density lipoprotein
WASI	Wechsler Abbreviated Scale of Intelligence
CGA	Computer Generated Arena

APPENDIX 10: Adverse Event Monitoring – UK Sites

Participants will be monitored closely for medication side effects with a diary and with laboratory testing as indicated in the Study Procedures section (see of the protocol (see Section 5). Adverse events will be addressed immediately. Participants will also be closely followed clinically at least once per month while on the study medication by the site physician. The Side Effects Checklist and Adverse Event Monitoring Form will be used to assess participants at every visit or phone contact.

An adverse event is the appearance or worsening of any undesirable sign, symptom, or medical condition occurring after the study has commenced, even if not considered to be related to the investigational medicinal product. Medical conditions/diseases present before starting the study will only be considered as adverse events if they worsen after the start of the study. Abnormal laboratory values or test results constitute adverse events only if they induce clinical signs or symptoms, are considered clinically significant, require therapy, or as specified on CTCAE, version 4.

The occurrence of adverse events will be sought by non-directive questioning of the patient during the study. Adverse events also may be detected when they are volunteered by the patient or through physical examination, laboratory test, or other assessment. As far as possible each adverse event will be evaluated to determine:

1. The severity (mild, moderate, severe)
2. Its relationship to the investigational medicinal product
3. Its duration
4. Action taken (no action taken; study drug dose adjusted/temporarily interrupted; study drug permanently discontinued; concomitant medication taken; non-drug therapy given; hospitalisation required)
5. Whether it is **serious**, where a serious adverse event (SAE) is defined as one which:
 - Is fatal or life-threatening
 - Results in persistent or significant disability/incapacity
 - Constitutes a congenital anomaly/birth defect
 - Requires prolonged hospitalisation (except where it is for routine treatment/monitoring, elective or pre-planned treatment not related to study, for social or respite reasons)
 - Is medically significant i.e. defined as an event that jeopardises the patient or may require medical or surgical intervention to prevent one of the above

Unlike routine safety assessments, SAEs are monitored continuously and have special reporting requirements (see below).

All adverse events will be recorded in detail, reported to the sponsor and treated appropriately. Such treatment may include changes in study drug treatment including possible interruption or discontinuation, starting or stopping concomitant treatments, changes in the frequency or nature

of assessments, hospitalisation, or any other medically required intervention. Once an adverse event is detected it will be followed until its resolution, and assessments will be made at each visit (or more frequently if necessary) of any changes in severity, the suspected relationship to the investigational medicinal product, the interventions required to treat it, and the outcome.

Evaluation of AEs and SAEs

Seriousness, causality, severity and expectedness will be evaluated for each AE. Cases that are considered serious, possibly, probably or definitely related to drug (i.e. serious adverse reactions, SARs) and unexpected (i.e. SUSARs) should be reported as described below.

Assessment of Seriousness

The Investigator should make an assessment of seriousness as defined above (see definitions).

Assessment of Causality

The Investigator must make an assessment of whether the AE/SAE is likely to be related to treatment according to the following definitions. All AEs/SAEs judged as having a reasonable suspected causal relationship (e.g. possibly, probably, definitely) to the study drug will be considered as ARs/SARs. If concomitant or rescue/escape drugs are given, the Investigator must also make an assessment of whether the AE/SAE is likely to be related to an interaction between the study drug and concomitant or rescue/escape drugs or whether the AE/SAE might be linked to either the study drug or concomitant or rescue/escape drugs but cannot be attributed to only one of these drugs. All AEs/SAEs judged as being related (e.g. possibly, probably, definitely) to an interaction between the study drug and concomitant or rescue/escape drugs, or any AE/SAE that cannot be attributed to only the study drug or the concomitant or rescue/escape drugs will also be considered to be ARs/SARs .

Unrelated: where an event is not considered to be related to the study drug.

Unlikely: the adverse event *is doubtfully related* to the study medication.

Possibly: although a relationship to the study drug cannot be completely ruled out, the nature of the event, the underlying disease, concomitant medication or temporal relationship make other explanations possible.

Probably: the temporal relationship and absence of a more likely explanation suggest the event could be related to the study drug.

Definitely: The known effects of the study drug or its therapeutic class, or based on challenge testing, suggest that study drug is the most likely cause.

Alternative causes such as natural history of the underlying disease, other risk factors and the temporal relationship of the event to the treatment should be considered and investigated.

Assessment of Severity based on CTCAE (version 4)

The Investigator will make an assessment of severity for each AE/SAE and record this on the Adverse Event (AE) Form according to one of the following categories:

Mild: an event that is easily tolerated by the participant, causing minimal discomfort and not interfering with every day activities.

Moderate: an event that is sufficiently discomforting to interfere with normal everyday activities.

Severe: an event that prevents normal everyday activities.

Assessment of expectedness

If an event is judged to be an AR/SAR, the evaluation of expectedness will be made based on knowledge of the reaction and the relevant product information documented in the Summary of Product Characteristics (SmPC).

Serious Adverse Event (SAE) reporting

Any SAE will be reported by the Principal Investigator (including a completed SAE form) within 24 hours of first knowledge to the Sponsor. The Principal Investigator will ensure that the patient is appropriately treated. They will also determine whether the SAE is a SUSAR (Suspected Unexpected Serious Adverse Reaction). If it is deemed to be a SUSAR it will be reported immediately to the sponsor. The Regulatory Competent Authority (MHRA) and Research Ethics Committee will also be informed in accordance with Trial regulations. An annual safety report will be sent by the Chief Investigator to the MHRA, the Ethics Committee and sponsor. Completed initial and follow-up Serious Adverse Event forms should be faxed to the sponsor on [name] and addressed „For the attention of the Quality Manager“. Alternatively, scanned forms can be emailed to [contact].

Regulatory Reporting Requirements

The sponsor, or their delegate, has a legal responsibility to notify the Regulatory Competent Authority and the Research Ethics Committee that approved the trial. Fatal or life threatening SUSARs will be reported no later than 7 calendar days, with a further 8 days for follow up information. All other SUSARs will be reported no later than 15 calendar days after the sponsor is first aware of the reaction.

Follow up procedures

After initially recording an AE or recording and reporting an SAE, the Principal Investigator is required to follow each participant until resolution. Follow up information on an SAE should be reported to the sponsor. AEs still present in participants at the last study visit should be monitored until resolution of the event or until no longer medically indicated.

Criteria for premature termination of study

These criteria include new safety data, or concerns from safety data (number and nature of SUSARs); or evidence from other studies.

Pregnancy

If the event that pregnancy does occur in a patient at any time between commencement of the study and 28 days after completion or termination of the study the pregnancy will be followed up to determine outcome, including spontaneous or voluntary termination, details of the birth, the presence or absence of any birth defects, congenital abnormalities, or maternal and/or newborn complications. Details of the pregnancy will be recorded on a Pregnancy Reporting Form. After

that the health of the baby will be followed up at 12 and 24 months old. Any SAE experienced during pregnancy will be reported on the SAE Report form.

All serious adverse events require immediate notification to the UK co-sponsor and US Operations Center. All adverse events, whether serious or otherwise, will be followed until resolution (the patients health has returned to his/her baseline status) or until the event has stabilized (investigator does not expect any further improvement or worsening of the adverse event). Participants withdrawn from the study due to adverse events will be followed by the investigator until resolution. All grade 3, 4 and 5 adverse events will be reviewed by the US Clinical Review Committee.

All adverse events will be tabulated by treatment arm, severity grade and reported to the US NF1 Data and Safety Monitoring Board (DSMB). The occurrence of adverse events will be reviewed by the DSMB at 2-month intervals to monitor patient safety. Summary details of the occurrences and grade of adverse events will be distributed to each site at 2-monthly intervals. In addition, all unexpected and serious adverse events will be forwarded to the US medical monitor, [name]. She will serve as a patient advocate, will be independent of the clinical study team, and will report to the DSMB. She will oversee the progress of the protocol, especially issues of individual subject/patient management and safety. The monitor will provide an unbiased written report of each event.

reassure the child that he/she is not expected to answer all the questions and it is only expected that he/she try his/her best on the task. All test administrators will have psychological training and experience with interacting and assessing children. If for some reason the child states that he/she does not want to continue, the assessment will cease. We will then consult with the parent and child to ascertain whether the testing will continue.

There are an estimated six partial or whole days that a child could miss school while participating in this trial. We will recommend to the parent (parents, legal guardians) that he/she should discuss school policies for excused absences and make necessary arrangements for make-up work.

7.0 Statistics

Determination of sample size: No data exist on the effects of Lovastatin in children with NF1. A clinical and meaningful difference for primary efficacy measures is defined as an effect size of one half of a standard deviation, which is classified as a treatment effect of medium magnitude (Cohen, 1988). A sample size of 64 participants per treatment group (128 total) will be sufficient to detect an effect size of half a standard deviation at the two-sided 0.05 significance level with power of 0.80 (Peat, Mellis, Williams & Xuan, 2001). To allow for a 10% dropout rate prior to the 16-week point, a total of 142 participants will be enrolled.

Interim analyses: Interim analyses will be done under the purview of the DSMB, which will set the content and frequency of analyses. We will propose a Charter containing a data monitoring plan that will include stopping guidelines. We expect these to be the Lan DeMets modifications of the O'Brien Fleming boundaries (Lan & DeMets, 1983; O'Brien & Fleming, 1979)). It is expected that the DSMB will review this charter during its first meeting.

Data analysis: Demographic and baseline characteristics will be summarized for each group using descriptive statistics. Intention-to-treat analyses will be conducted for the primary outcomes measures. An intention-to-treat analysis provides an unbiased, conservative and consistent estimate of a treatment effect (Heritier, Gebiski & Keech, 2003).

Analyzing change scores from baseline to post-treatment does not control for baseline imbalance because of the regression to the mean (Vickers & Altman, 2001). Also, with changes scores, if the treatment is effective, the statistical significance of the treatment effect will depend upon the correlation between baseline and follow-up scores. Therefore, to determine whether there has been a significant change from baseline to post-treatment, primary and secondary outcomes will be analyzed using ANCOVA, which is a better approach than analyzing change scores with independent t-tests (Vickers & Altman, 2001).

In addition, at an individual case level to determine whether test-retest change scores from baseline to post-treatment are reliable and clinically meaningful, standardized regression based

change scores (RBC) will be also be calculated. RBC can account for measurement error, differential practice effects and regression to the mean (Sherman et al., 2003). However, RBC scores do not necessarily indicate whether a significant change from baseline has occurred (Sherman et al., 2003). Similar statistical analysis will be conducted for scores from post-treatment to follow-up. Linear mixed models may also be conducted to examine changes over time. In addition, a number of sub-group analyses are planned to help identify individuals more likely to benefit from, or be harmed by, the treatment. In regard to treatment effects, definition of subgroups will rely on baseline data, not data measured after randomization. Such subgroups might include age (including comparison of 8-9 years to 10 years and older), gender, and presence of ADHD (on or off stimulant medication) (if there are sufficient cases). Exploratory data derived through subgroup analyses will serve primarily to generate new hypothesis for subsequent studies.

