affected by Lovastatin. Second, the CANTAB has evolved from animal behavior paradigms to facilitate cross-species studies of cognition. As such, it has strong theoretical underpinnings. Third, it has been designed with a neural systems approach in mind, being extensively validated in patients with damage in specific areas of the brain. Fourth, it has extensive functional neuroimaging data available, outlining the neural substrates involved in many of the subtests, providing a useful confirmation of the neuroanatomical basis of the tests. Fifth, the tests are entirely computerized, enabling automatic recording of response accuracy and latencies via a touch-screen apparatus. This increases the consistency of data collection between sites. In addition, there are five equivalent forms available, minimizing retest practice effects. Subtests from the CANTAB start at a simple level and gradually increase in difficulty. Finally, research suggests that computerized batteries, in particular the CANTAB, are sensitive to subtle neurocognitive changes and may be better able to detect subtle cognitive dysfunction and changes over time than traditional paper-and-pencil neuropsychological measures (Bedard et al., 2004; Froestl, Gallagher, Jenkins, Madrid, Melcher et al., 2004; Makdissi, Collie, Maruff, Darby, Bush et al., 2001; Nestor, Scheltens & Hodges, 2004).

In this study, the primary outcome measures have been selected based on the effects of Lovastatin in murine models of NF1 and the cognitive functions that are frequently impaired in children with NF1. Therefore, the primary outcome measures assess visual spatial learning and sustained attention. Visual spatial learning will be assessed using the Paired Associate Learning (PAL) subtest from the CANTAB (see Section 5.1.4.1). Preliminary findings indicate that 46% (13/28) of children with NF1 performance on the PAL is impaired (>1SD below normative mean; Payne, Barton & North, unpublished data). Sustained attention will be assessed using the Score! subtest from the Test of Everyday Attention for Children (TEA-Ch). Previous findings indicate that 63% (50/80) of children with NF1 have impaired performance (>1SD below normative mean) on the Score! subtest (Hyman et al., 2005).

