2.0 Research Plan

2.1 Specific Aim

The specific aim of this study is to determine whether Lovastatin significantly improves visual spatial learning and/or sustained attention in children with NF1.

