2.3 Hypotheses

It is hypothesized that Lovastatin will improve the visual spatial memory and/or attention deficits in children with NF1. This is based on studies demonstrating that Lovastatin has significantly improved impairments in visual spatial memory and attention in the NF1 murine model.

It is further expected that Lovastatin will be safe and well tolerated over a 16-week period.

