5.1.4.1 Primary Outcome Measures

The effect of Lovastatin on cognitive functioning in children with NF1 has not been examined. Evidence from a murine model of NF1 suggests Lovastatin improves visual spatial learning and memory, and attention. As such, the following primary outcome measures are:

- Visual Spatial Learning and Memory

*CANTAB Paired Associate Learning (PAL)

PAL is a measure of arbitrary visuospatial associations. It involves the randomized „opening“ of six boxes that are displayed on the screen, each revealing a different pattern. Immediately after presentation of the six patterns, each item reappears in the central box in random order and the participant has to indicate where each item was first seen. Measures include the number of patterns placed correctly on the first trial and the number of repeat presentations needed to learn all the associations correctly. Administration time for this measure is approximately 10 minutes.

- Attention

*Score! Subtest from the Test of Everyday Attention for Children (TEA-Ch: Manly, Robertson, Anderson & Nimmo-Smith, 1999).

The TEA-Ch is a normed and standardized multi-subtest battery that assesses various aspects of attentional function in children aged between 6 years and 15 years 11 months. The Score! subtest requires children to keep count of sounds they hear on a tape. This task does little to „grab“ the child's attention and is a measure of their ability to self-sustain his or her own attention. Previous findings indicate that approximately 63% of children with NF1 are impaired on Score! (Hyman et al., 2005). There are two alternate forms for this subtest and it takes approximately 8 minutes to complete.

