7.0 Statistics

Determination of sample size: No data exist on the effects of Lovastatin in children with NF1. A clinical and meaningful difference for primary efficacy measures is defined as an effect size of one half of a standard deviation, which is classified as a treatment effect of medium magnitude (Cohen, 1988). A sample size of 64 participants per treatment group (128 total) will be sufficient to detect an effect size of half a standard deviation at the two-sided 0.05 significance level with power of 0.80 (Peat, Mellis, Williams & Xuan, 2001). To allow for a 10% dropout rate prior to the 16-week point, a total of 142 participants will be enrolled.

Interim analyses: Interim analyses will be done under the purview of the DSMB, which will set the content and frequency of analyses. We will propose a Charter containing a data monitoring plan that will include stopping guidelines. We expect these to be the Lan DeMets modifications of the O'Brien Fleming boundaries (Lan & DeMets, 1983; O'Brien & Fleming, 1979)). It is expected that the DSMB will review this charter during its first meeting.

Data analysis: Demographic and baseline characteristics will be summarized for each group using descriptive statistics. Intention-to-treat analyses will be conducted for the primary outcomes measures. An intention-to-treat analysis provides an unbiased, conservative and consistent estimate of a treatment effect (Heritier, Gebiski & Keech, 2003).

Analyzing change scores from baseline to post-treatment does not control for baseline imbalance because of the regression to the mean (Vickers & Altman, 2001). Also, with changes scores, if the treatment is effective, the statistical significance of the treatment effect will depend upon the correlation between baseline and follow-up scores. Therefore, to determine whether there has been a significant change from baseline to post-treatment, primary and secondary outcomes will be analyzed using ANCOVA, which is a better approach than analyzing change scores with independent t-tests (Vickers & Altman, 2001).

In addition, at an individual case level to determine whether test-retest change scores from baseline to post-treatment are reliable and clinically meaningful, standardized regression based

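### Two primary outcomes and an and/or aim, but no rule in section 7.0 for what counts as success across them

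*SAP*

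**What the plan says.** Protocol 1.9 names two primary domains: "Therefore, the primary outcome measures assess visual spatial learning and sustained attention". They are measured by CANTAB PAL and TEA-Ch Score!, and Protocol 5.1.4.1 and Appendix 5 confirm both as primary. The aim in Protocol 2.1 is to "determine whether Lovastatin significantly improves visual spatial learning and/or sustained attention in children with NF1". The hypothesis in 2.3 is that "Lovastatin will improve the visual spatial memory and/or attention deficits in children with NF1".

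Section 7.0 reads the same in the Protocol and the SAP. It sizes the trial at 64 per group for "half a standard deviation at the two-sided 0.05 significance level with power of 0.80". On analysis it says that "primary and secondary outcomes will be analyzed using ANCOVA, which is a better approach than analyzing change scores with independent t-tests". It gives no split of alpha, testing order, composite, requirement that both succeed, or statement that each outcome is claimed separately. Its only error control concerns interim looks: "We expect these to be the Lan DeMets modifications of the O'Brien Fleming boundaries". Its only exploratory label is for subgroups: "Exploratory data derived through subgroup analyses will serve primarily to generate new hypothesis for subsequent studies".

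Protocol 5.1.4.1 also leaves the PAL variable open: "Measures include the number of patterns placed correctly on the first trial and the number of repeat presentations needed to learn all the associations correctly". It does not say which of these is tested.

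**The concern.** The aim calls for a yes or no answer. If one outcome is significant and the other is not, the plan cannot supply it. The error rate and power of the primary conclusion then depend on a choice that could be made after the data are seen. Reading the aim literally raises the chance that an inactive drug succeeds; requiring both outcomes lowers power below the planned 0.80. The two PAL measures widen the room for choice. Protocol 9.2 says that an efficacious result will lead to a Phase III study, so the answer has a consequence.

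**Working it through.** **Inputs from section 7.0:** difference 0.5 SD, 64 per group, two-sided 0.05, power 0.80, 10% dropout, 142 enrolled. **Assumed, because the documents give no value:** correlation ρ between the two outcomes (0, 0.3, 0.5, 0.9) and baseline to week-16 correlation r (0.3, 0.5). Interim looks are ignored until step 7.

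**1. The plan's own figure.** Noncentrality is 0.5 × √(64/2) = 2.83 with 126 degrees of freedom; power at two-sided 0.05 is 0.8015. Solving for 0.80 gives 63.8, so 64 per group. Dropout: 128/0.9 = 142.2, against 142 stated. The figure is right for one outcome at the full 0.05.

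**2. Either suffices, each at 0.05, drug inactive.** False benefit is 1 − P(Z₁ < 1.96, Z₂ < 1.96); at ρ = 0 this is 1 − 0.975² = 4.94%. Rejection in either direction is 1 − P(|Z₁| < 1.96, |Z₂| < 1.96); at ρ = 0 this is 1 − 0.95² = 9.75%. Holm's error with both outcomes null uses the second formula with the 0.025 critical value.

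| ρ | False benefit, either suffices | Any rejection, either suffices | Any rejection, Holm |
|---|---|---|---|
| 0 | 4.94% | 9.75% | 4.94% |
| 0.3 | 4.76% | 9.51% | 4.84% |
| 0.5 | 4.54% | 9.07% | 4.65% |
| 0.9 | 3.52% | 7.04% | 3.62% |

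The reference for one test is 2.5% for false benefit and 5% for any rejection.

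**3. Both required, each at 0.05.** False benefit is 0.025 + 0.025 minus the first error column: 0.06%, 0.24% and 0.46% at ρ = 0, 0.3 and 0.5. Power when both respond is 0.8015² = 0.642 at ρ = 0, then 0.669 and 0.689 (simulated t statistics).

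**4. Each outcome claimed only for itself.** Each claim has 2.5% false-benefit error (5% two-sided).

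**5. Power at 64 per group under the proposed rules (unadjusted t-test).** If only one outcome responds, it must in effect pass 0.025, with power 0.712. If both respond:

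| ρ | Holm, per outcome | Holm, both | Fixed 0.025, per outcome | Fixed 0.025, both | At least one, either rule |
|---|---|---|---|---|---|
| 0 | 0.78 | 0.63 | 0.71 | 0.51 | 0.92 |
| 0.3 | 0.77 | 0.66 | 0.71 | 0.54 | 0.88 |
| 0.5 | 0.77 | 0.68 | 0.71 | 0.57 | 0.85 |
| 0.9 | 0.75 | 0.73 | 0.71 | 0.65 | 0.77 |

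As a check, for each rule the chance of at least one success is twice the per-outcome power minus the chance of both. For fixed 0.025 at ρ = 0.9 that is 2 × 0.712 − 0.650 = 0.774.

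**6. Gain from ANCOVA.** The standardised effect becomes 0.5/√(1 − r²): 0.524 at r = 0.3 and 0.577 at r = 0.5. Power at 0.025 (125 degrees of freedom) rises from 0.71 to 0.756 and 0.839.

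**7. Interim looks.** With 0.025 per outcome and a Lan-DeMets O'Brien-Fleming boundary (normal approximation, assumed timings), power is 0.721 with no look, 0.720 with one look at half the information and 0.717 with looks at thirds. The looks themselves cost little. Moving from Holm to fixed 0.025 costs more, as the table in step 5 shows.

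**The case against.** Either-suffices is not written anywhere. The same and/or wording describes whom the trial enrols (Protocol 1.10, 4.1, 4.2), so in the aim it may only echo eligibility or list two separate questions. Section 7.0 defines the half-SD difference for efficacy measures in the plural, which also fits a separate claim for each. This stands: only the missing rule is established, and every inflated error rate is conditional on one reading.

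A reader might infer that the chance of a false claim of efficacy is nearly 10%. The documents do not support that. The 9.75% to 7.0% counts results in which lovastatin looks worse, and these cannot meet an aim of improvement. The like-for-like comparison is 4.9% to 3.5% against 2.5%.

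A reader might also infer that the sample size is wrong. It is not: 0.80 is correct for each outcome at 0.05.

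The trial is Phase II, and success leads to a further trial rather than directly to a treatment claim. That can justify a lenient rule, but not the absence of one, since the plan sets a two-sided 0.05 level and an aim of significant improvement. The DSMB charter is not among the documents and its content is unknown. As section 7.0 describes it, the charter concerns data monitoring and stopping guidelines, and boundaries for repeated looks do not settle how two outcomes are combined.

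**Conclusion.** The concern holds: two primary outcomes, an and/or aim, one 0.05 level and no rule joining them. That finding rests on the text alone. Its size depends on the rule later chosen and on assumed correlations. Under either-suffices, an inactive drug meets the aim in 4.9%, 4.8%, 4.5% and 3.5% of trials at correlations 0, 0.3, 0.5 and 0.9, instead of 2.5%. Under both-required, power is 0.64 to 0.69 for correlations 0 to 0.5. Under separate claims, each claim keeps its nominal error. The rule must be written before unblinding, because a rule chosen afterwards gives no protection.

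**What to change.** In section 7.0 of both documents, before unblinding, add:

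*PAL and Score! are tested with Holm's procedure at a family-wise two-sided 0.05: the smaller p-value is compared with 0.025 and, if significant, the other with 0.05. The aim is met if at least one is significant in favour of lovastatin. If the charter includes efficacy looks, each outcome is tested at two-sided 0.025 with its own Lan-DeMets O'Brien-Fleming boundary, unless the charter defines a group-sequential Holm procedure.*

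In Protocol 5.1.4.1, name the one PAL score to be tested, so that the family is two tests.

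Restate power for 64 per group and half an SD (unadjusted t-test, ignoring looks):
- 0.80 per outcome at 0.05, and 0.71 at 0.025 if only one outcome responds.
- If both respond, at correlations 0 to 0.9, Holm gives 0.78 to 0.75 per outcome and 0.92 to 0.77 for at least one. Fixed 0.025 gives 0.71 per outcome, 0.51 to 0.65 for both, and the same figures as Holm for at least one.
- The ANCOVA gain may be shown as a range but should not be relied on. Children enter on low screening scores on the primary measures, which may lower the baseline to week-16 correlation.

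The cost is wording in the Protocol, SAP and charter, a stricter first threshold and a less favourable stated power. No added patients are proposed. Another pre-specified rule that controls family-wise error would also close the gap.
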